### 3.1 Study Population

#### 3.1.1 Inclusion criteria:

- Primary caregivers of all pediatric patients (0-17 years old) with **acute appendicitis**, including both perforated and non-perforated appendicitis cases, who have undergone an **urgent** appendectomy.
- Primary caregivers of all pediatric patients (0-17 years old) with **umbilical** or **inguinal hernias** who have undergone an **elective** surgical repair.

#### 3.1.2 Exclusion criteria:

- Patient or family does not understand English or French (education material available in only these two languages).
- Patient presenting for an elective interval appendectomy.
- Patient presenting with an incarcerated or strangulated hernia requiring emergency surgical repair.

### 3.2 Period studied

We anticipate a period of enrollment of approximately 6 months for each surgical procedure, as specified above in Section 3. We will aim to have 100 patients for the Pre-Implementation Phase & 100 patients for the Post-Implementation Phase.

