#### 1.1.2 Elective Surgery – Inguinal and Umbilical Hernias

For the elective surgical setting, we have chosen to target patients with umbilical and inguinal hernias who are booked for elective surgical repairs. Inguinal hernias occur in approximately 3-5% of term infants and 13% of infants born at less than 33 weeks gestational age. Inguinal hernias are commonly repaired to avoid incarceration of the hernia, and at the MCH we perform approximately 240 inguinal hernia repairs per year. Umbilical hernias are also one of the more common pediatric conditions, occurring in approximately 1 in every 6 children. However, they are more likely to close spontaneously and resolve without surgery than inguinal hernias. Nevertheless, some umbilical hernias do cause symptoms and may also fail to regress, thus necessitating surgical repair. At the MCH, we perform approximately 140 umbilical hernia repairs per year.

We hope that by testing the impact of education tools on such a large sample of patients, we will demonstrate an accurate measure of our primary outcome and continue to improve our patient-centered care practices in the realm of pediatric surgery. Furthermore, we believe that this study will serve as further evidence in support of a movement towards ERAS protocols and standardized care pathways in pediatric surgical centers.

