#### 1. Pilot Phase (2-3 weeks) – Validation of Questionnaire

- A convenience sample of 5 patients with acute appendicitis and their families will be selected during their routine postoperative visits to provide input on the questionnaire. The preliminary questionnaire is attached, and was developed by the authors based on the Amsterdam Preoperative Anxiety and Information Scale (APAIS), Productivity and Disease Questionnaire (PRODISQ), the Health and Labor Questionnaire (HLQ), and a literature review.
- A convenience sample of 5 surgeons and 5 nurses will also be solicited to provide feedback.
- The questionnaire will be adapted based on qualitative feedback from the participants listed above.

2. Pre-Implementation Phase (100 patient/approx. 6 months)

- All patients with acute appendicitis who undergo appendectomies will be eligible to participate, and families will be consented prior to surgery. The parental anxiety assessment will be done only before surgery with the Amsterdam Preoperative Anxiety and Information Scale (APAIS). In addition, the email of one of the primary caregivers will be collected, and the caregiver will receive an email with a link to the post-operative questionnaire 10 days post-discharge. At 14 days post-discharge, they will receive a reminder email with the link to the questionnaire. All responses to the questionnaire are voluntary and anonymous.

Before Surgery	Obtain Consent
	Amsterdam Preoperative Anxiety and Information Scale (APAIS)
	Collection of email of primary caregiver
10 days Post-operative	Link to Parental Productivity Survey will be sent
14 days Post-discharge	Reminder email with link to the questionnaire will be sent.

3. Post-Implementation Phase (100 patient/approx. 6 months)

- The education tool will be distributed to families whose child is undergoing an appendectomy. The parental anxiety assessment will be done in the same way as above, only before surgery with the Amsterdam Preoperative Anxiety and Information Scale (APAIS). In addition, the email of one of the primary caregivers will be collected, and the caregiver will receive an email with a link to the post-operative questionnaire 10 days post-discharge. At 14 days post-discharge, they will receive a reminder email with the link to the questionnaire. All responses to the questionnaire are voluntary and anonymous.

Before Surgery	Obtain Consent
	Amsterdam Preoperative Anxiety and Information Scale (APAIS)

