## **4 DATA ANALYSIS**

The primary outcome that will be assessed is the loss of parental productivity measured in hours of paid or unpaid work missed due to caring for a child in the post-operative recovery period in caregivers who received the education tool compared to those who did not. Secondary outcomes that will be assessed include: household income (dollar amount) lost due to indirect productivity losses, hours of sleep lost, hours of leisure time lost, number of times that medical assistance is sought in the post-operative period, and need for compensated or non-compensated help at home.

Bivariate analysis will be performed using 2 sample t-tests for dichotomous predictor variables, Fisher's exact test or one-way ANOVA for categorical predictor variables, and Pearson correlation for continuous predictors where appropriate. A p-value of < 0.05 will be deemed statistically significant.

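### The primary outcome exists only for caregivers who answer a voluntary emailed survey with one reminder, and the target of 100 per phase makes no allowance for non-response

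*Combined protocol and SAP*

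**What the plan says.** **Size.** Section 3.2: "We will aim to have 100 patients for the Pre-Implementation Phase & 100 patients for the Post-Implementation Phase". Section 3 attaches the same number to each phase, for example "Pre-Implementation Phase (100 patient/approx. 6 months", and says of eligible cases that "families will be consented prior to surgery". Neither section says whether the number counts enrolled families or completed questionnaires. Neither says clearly whether it applies to each procedure or overall.

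**Primary outcome.** Section 4: "The primary outcome that will be assessed is the loss of parental productivity measured in hours of paid or unpaid work missed".

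**Source of the data.** Section 3, in both phases: "the caregiver will receive an email with a link to the post-operative questionnaire 10 days post-discharge". Then: "At 14 days post-discharge, they will receive a reminder email with the link to the questionnaire". And: "All responses to the questionnaire are voluntary and anonymous". Section 5.3 repeats the email and the single reminder, and adds that answers will not be tied to email addresses.

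**Not stated.** The documents give no expected reply rate, non-response allowance, missing-data plan, power calculation, SD for hours missed, or target interval width. Section 1.1 says this loss has never been measured in a pediatric surgical setting.

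**The concern.** Families enter the study before surgery, when no primary-outcome data exist. Those data arrive only if the caregiver later opens an email and chooses to answer. If the 100 counts families who enter, the number in the primary analysis is 100 times the reply rate, and the plan neither states nor protects that rate.

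Two things are at stake. The first is precision: fewer replies widen the interval on the difference in hours missed. The second is selection: caregivers who reply may differ from those who do not. Because answers are unlinked from emails, this cannot be examined person by person afterwards. Replying might also differ between phases, since caregivers after implementation are sent two surveys and those before implementation one. The documents give no data on whether it would.

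The anxiety scale is completed before surgery, so this point concerns only the outcomes collected by email.

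**Working it through.** **1. Is there a figure to reproduce?** No. The 100 per phase is given without effect size, SD, power or reply rate, so it cannot be re-derived. What follows shows only how precision depends on replies.

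**2. What does the 100 count?** Section 3.2 speaks of enrollment, Section 3 ties the number to phases in which families consent before surgery, and Section 3.4 ties duration to recruitment. All three point to enrolled families, but none says so.

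The other reading can be checked against the annual volumes in Sections 1.1.1 and 1.1.2, taking about 6 months per phase as in Section 3. For 100 *replies* per phase in each procedure:
- Appendectomy: 300/2 = 150 cases, and 100/150 = 67% of all cases would have to consent and reply.
- Inguinal hernia: 240/2 = 120 cases, and 100/120 = 83%.
- Umbilical hernia: 140/2 = 70 cases, which cannot supply 100 on either reading.

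So counting replies would be demanding for two procedures. The umbilical figure does not separate the readings, but it shows that the plan needs to say whether the target is per procedure or overall.

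**3. Precision by number of replies.**
Inputs from the documents: 100 per phase (Section 3.2); two-sample t-test and 0.05 level (Section 4).
Assumptions: 100 means enrolled; a single procedure; two-sided test; equal reply rates in the two phases; reply rates as shown; 80% power for the last column.

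Half-width of the 95% interval, in SD units: t(0.975, 2n−2) × √(2/n).
- n = 100: 1.972 × 0.1414 = 0.279
- n = 70: 1.977 × 0.1690 = 0.334
- n = 50: 1.984 × 0.2000 = 0.397

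| Replies per phase | 95% CI half-width (SD) | Detectable difference at 80% power (SD) |
|---|---|---|
| 100 | 0.28 | 0.40 |
| 80 | 0.31 | 0.45 |
| 70 | 0.33 | 0.48 |
| 60 | 0.36 | 0.52 |
| 50 | 0.40 | 0.57 |
| 40 | 0.45 | 0.63 |

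Against full reply, the interval is 0.334/0.279 = 1.20 times as wide with 70 replies and 0.397/0.279 = 1.42 times as wide with 50. The SD of hours is unknown, so none of this converts to hours.

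**4. What might more reminders buy?** If they raised replies from 50 to 60 per phase (an assumed gain), the half-width would fall from 0.397 to 0.362 SD, a ratio of 0.91, so about 9% narrower.

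**5. Could recruitment be raised instead?** To obtain 100 replies, enrol 100/reply rate: 100/0.7 = 143, or 100/0.5 = 200. Six months of appendectomies, about 150 cases, would allow 143 only with almost every family enrolled, and would not allow 200. Section 3.4 allows 12 to 24 months, so this is possible, but slower and costlier than extra emails.

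**The case against.** **The size claim.** A reader might infer that the trial cannot deliver what Section 1.1.2 promises, where the authors hope that with "such a large sample of patients, we will demonstrate an accurate measure of our primary outcome". The documents do not support that. The sentence is a hope in the background section, follows the hospital's annual case volumes, and is not tied to 100 per phase. With no power or interval target stated, there is no threshold to miss. Fewer replies make an estimate less precise, but do not in themselves make it inaccurate.

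**The unit.** A reader might also take it as fact that Section 3.2 counts consented patients and that the analysis will therefore fall short. The section says only patients, and Section 3.3 goes on to describe collecting questionnaire answers for each patient, which is compatible with counting repliers. Enrolled families is the likelier reading, but it remains an inference.

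**Pooling.** Section 3 says the phases are similar for all three procedures, and Section 4 compares caregivers with and without the tool without splitting by procedure. If the target is 100 per phase per procedure and the analysis is pooled, 50% reply leaves 3 × 50 = 150 per phase. The half-width is then 1.968 × √(2/150) = 0.23 SD, better than the single-procedure best case of 0.28. The documents do not settle this, so the table is an illustration and not a forecast.

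**The reminders.** Later emails fall outside the 10 to 14 days after discharge named in Section 2.1. Unlinked answers mean reminders cannot be aimed at non-repliers, which invites duplicates. Section 5.3 describes one reminder, so a change would plausibly need ethics review. More reminders also need not reduce selection bias. The first three objections can be met by the wording of the fix. The last stands: a higher reply rate limits the room for bias but does not guarantee less of it.

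**Conclusion.** The point holds as a cheap improvement. The only source of the primary outcome is a voluntary, anonymous emailed survey with one reminder, and the target makes no allowance for unanswered surveys. If the 100 counts enrolled families in one procedure, the half-width of the primary comparison grows from 0.28 SD with full reply to 0.33 SD at 70% and 0.40 SD at 50%.

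The conclusion that non-response costs precision needs only the first reading of the 100. Its size rests on assumed reply rates, a two-sided test and no pooling across procedures. The documents do not show that the trial is too small or that a stated precision will be missed. Because individual comparison of repliers with non-repliers is ruled out by the unlinked design, effort is best spent on raising the reply rate in advance.

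**What to change.** **In Sections 3 and 5.3**, add two further automatic reminder emails, for example at days 17 and 21 after discharge, identical in both phases. Send them to everyone with a request to ignore them if already answered, or use single-use anonymous links so that no caregiver can reply twice.

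**In the questionnaire**, ask every caregiver, whenever they reply, for hours missed over the same fixed period after discharge, inside the two-week window of Section 1.1. The period should end no later than the day the link is sent, so that the earliest repliers can cover it in full. This needs one agreed sending date: the Section 3 text counts 10 days from discharge, the Section 3 tables give 10 days post-operative, and one sentence in Section 5.3 says one week after discharge.

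**In reporting**, give the number of surveys sent and returned in each phase. Anonymity permits these counts.

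**In Section 3.2**, say whether 100 means enrolled or responding caregivers, and whether it applies per procedure or overall.

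**Cost.** Two automated emails, some protocol and questionnaire wording, a minor ethics-board amendment, and a slightly longer recall delay for late repliers. No extra patients are needed. The change should be in place before the pre-implementation phase starts, so that both phases are handled alike.

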### 3.3 Description of data being retrieved

For each patient, we plan to collect answers from the circulated questionnaires, which will include questions related to the child and caregiver. This survey will not collect any identifiable information. However, we will collect some patient/parent information including:

- Age of the child and caregiver
- Relation of the caregiver to the child
- Caregiver's education level
- Caregiver's yearly income
- Caregiver's work hours

To assess indirect resource use (productivity losses) we will collect the following information:

- Hours absence from paid or unpaid job
- Loss of leisure time and sleep
- Access to compensated or uncompensated help at home
- Number of follow ups with medical personnel during the child's recovery
- Utility of education tool

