### **5.2 Confidentiality**

Only data relevant to this study as outlined in this protocol will be collected by the research team. All the information collected during the research project will remain confidential to the extent required and provided by law.

The data collected from the online surveys will be stored in a digital file on a password protected computer behind the MUHC firewall for 7 years following the completion of the study. The data will then be destroyed. No personal or identifiable information will be collected from patients.

We foresee no ethical issues that would prevent the conduct of this study. The patient education tool is being implemented as part of a continuous process for ongoing improvement in our pediatric surgery division, with the ultimate goal of providing the highest quality of patient- and family-centered care. Survey participation is voluntary and anonymous, with no negative impact from non-participation. This study does not change the current clinical practice guidelines for appendicitis.

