### **5.3 Informed consent**

All patients and their families who undergo an operation for acute appendicitis, umbilical hernia, and inguinal hernia will be eligible for the research study and invited to complete the anxiety scale and to take the survey 10 days after discharge from the hospital. Informed consent will be obtained prior to surgery. The primary caregiver will be asked to provide us with their email address.

They will be emailed a link to an online questionnaire(s) 10 days after their discharge. They will be emailed a reminder email and link to the online questionnaire 14 days after discharge.

The answers collected from questionnaire will be anonymous, and no patient identifiable information will be collected. However, we will be collecting some sensitive information about the caregiver, including their average annual income. Furthermore, we require their email addresses to facilitate the distribution of the online surveys one week post-discharge of the child. Therefore, we will obtain informed consent from the patient and caregiver during the patient's hospitalization.

Participation in the survey is anonymous. This means that although emails will be obtained to facilitate the distribution of the surveys, the answers will not be linked to the patient or caregiver's emails and therefore the research team will not be able to trace the answers back to the patients or caregivers. This ensures patient and caregiver anonymity.

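### As scheduled, no APAIS score can be joined to the listed child and caregiver characteristics, and survey non-responders can be counted but not described

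*Combined protocol and SAP*

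**What the plan says.** **Before surgery.** Section 3 lists the same three preoperative steps in the pre- and post-implementation phases: consent, APAIS and an email address. The text for the pre-implementation phase reads "The parental anxiety assessment will be done only before surgery with the Amsterdam Preoperative Anxiety and Information Scale (APAIS" and then "In addition, the email of one of the primary caregivers will be collected". Neither phase lists a demographic or clinical form.

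**After discharge.** Section 3.3 says "we plan to collect answers from the circulated questionnaires, which will include questions related to the child and caregiver". It goes on to call this a survey without identifiable content, and continues "However, we will collect some patient/parent information including", followed by child and caregiver age, relation to the child, education, yearly income and work hours. Section 5.3 gives the timing: "They will be emailed a link to an online questionnaire(s) 10 days after their discharge", with a reminder at day 14. Section 3 adds "All responses to the questionnaire are voluntary and anonymous".

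**Linkage.** Section 5.3 states that "the answers will not be linked to the patient or caregiver's emails and therefore the research team will not be able to trace the answers", so no survey answer can be tied to a family. Section 5.2 adds "No personal or identifiable information will be collected from patients" and limits collection to what the protocol outlines. No study ID, chart extraction or screening log is described.

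**Analysis.** Section 4 plans bivariate tests only. It has no adjusted model and no comparison of responders with non-responders.

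**The concern.** Parental anxiety is in the objectives, the hypothesis and the study question (Sections 2.1 to 2.3). It is to be compared between two groups enrolled one after the other, each over about six months, without randomisation. Any change over that time in who brings the child, in caregiver education or in the children's ages could shift APAIS with no contribution from the education tool. The usual defence is to record such characteristics with the outcome and adjust for them. The schedule appears to record them elsewhere, later, only in those who choose to answer, and in a file that cannot be joined to APAIS.

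The same arrangement limits what can be said about survey non-response. The primary outcome, hours of work missed, is observed in responders only. If the families who answer are selected differently in the two phases, the comparison is biased, and the planned data give no picture of those who did not answer.

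The timing makes this worth raising now. An analysis plan can be amended until the data are analysed, but a characteristic that was never recorded with the score cannot be added afterwards.

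**Working it through.** The plan gives no figure to reproduce. It states 100 per phase (Section 3.2) without an effect size, SD, power or response rate. The check therefore traces each item to its collection point and then illustrates size under stated assumptions.

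**1. Where each item is collected**

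| Item | Collected | Source |
|---|---|---|
| Consent, APAIS, email | Before surgery, both phases | Section 3 |
| Child and caregiver age, relation, education, income, work hours | Circulated survey | Section 3.3 |
| Hours missed and other productivity items | Circulated survey | Section 3.3 |
| Link between survey answers and family | None | Section 5.3 |

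APAIS and the characteristics are in separate records with no key. Hours missed and the characteristics are in the same record.

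**2. What adjustment of APAIS would need.** For a two-level characteristic, the bias in the crude phase difference is

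(share in post phase − share in pre phase) × (mean APAIS at one level − mean APAIS at the other).

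The survey can show the first factor, among responders only. The second needs the characteristic and APAIS on the same caregiver, which the schedule never produces. A marked change in mix might be seen at group level, but its effect on APAIS could not be estimated or removed.

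**3. How many caregivers would be undescribed.** With 200 enrolled and response rate r (assumed), the number is 200 × (1 − r): 40 at 80%, 80 at 60% and 120 at 40%. Section 3.2 does not settle whether 100 per phase applies to each procedure, so read these as counts per 200 enrolled.

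**4. What selective response could do to the primary comparison.** Let D be the responder minus non-responder difference in mean hours missed, in SD units (assumed 0.2 to 0.5). Within a phase, the responder mean differs from the enrolled mean by (1 − r) × D. The bias in the phase contrast is the difference of these terms.

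- Gap in one phase only, 60% response there: 0.4 × 0.2 = 0.08 to 0.4 × 0.5 = 0.20 SD.
- Gap in one phase only, 40% response there: 0.6 × 0.2 = 0.12 to 0.6 × 0.5 = 0.30 SD.
- Same gap in both phases, 60% and 40% response: (0.6 − 0.4) × D = 0.04 to 0.10 SD in size.
- Same gap in both phases, 60% response in both: 0.

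Equal response rates are therefore compatible with no bias or with 0.08 to 0.20 SD. Counting responses does not settle the matter.

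**5. Precision.** If the added items explained a share R² of APAIS variance, the standard error would fall by 1 − √(1 − R²): 5.1% at R² = 0.10 and 10.6% at R² = 0.20. Both values of R² are assumed.

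**6. Risk of matching if items are repeated on both forms.** With K equally likely answer combinations and 100 caregivers in a phase, the share whose combination is unique is (1 − 1/K)^99: 61% at K = 200 and 87% at K = 720 (both K assumed). Finely recorded items would act as a matching key, so the bands must be coarse.

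**The case against.** The best reply is that the decisive form is not in view. Section 3 says the preliminary questionnaire is attached and names APAIS among its sources, and Section 3.3 speaks of questionnaires in the plural without giving a time for the characteristics. They could sit beside APAIS. This stands as a condition on the point. It does not remove it: the plural fits equally well the two post-discharge surveys of the post-implementation phase, and neither preoperative schedule lists any such item.

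Three stronger readings are tempting and are not supported.

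- *APAIS carries no covariate at all.* Phase is known when APAIS is completed, and presumably procedure. What is absent is the listed child and caregiver characteristics.
- *Nothing is known about non-responders, and differential non-response cannot be checked.* Surveys returned over links sent gives a response rate for each phase. Non-responders also contribute APAIS scores, although these cannot be told apart from those of responders.
- *The primary comparison cannot be adjusted.* It can, among responders, because outcome and characteristics share a survey. That Section 4 plans no adjustment is a gap in the analysis plan, not a result of where the items are asked.

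It is also fair to say that APAIS is not among the outcomes in Section 4, so the lost adjustment falls on an endpoint with no stated analysis. That is a separate and prior gap. Anxiety remains in the study question, and the gap should be closed in any case.

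Finally, anonymity is deliberate. Any remedy has to respect it, and step 6 shows that repeating detailed items would strain it.

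**Conclusion.** The point holds conditionally. As the schedule is written, and unless the attached form already carries the items, none of about 200 APAIS scores can be joined to a listed characteristic. The anxiety comparison between phases can then only be crude with respect to those characteristics. Non-responders can be counted but not described; how many there would be, and the bias of up to 0.30 SD they could cause, rest on the response rates and gaps assumed above and are not predictions. Confounding and undescribed non-response are the reasons to act; the gain in precision is modest.

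A reader might also infer that asking usual work hours before surgery would give a better reference for hours missed. With unlinked forms it would not, because the preoperative answer could not be joined to that caregiver's later report.

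This weakens a named objective and the check on who supplies the primary outcome. It does not make the study invalid.

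**What to change.** First, state in Section 3.3 which form carries each item and when. If the preoperative form already has the characteristics, saying so answers most of the point.

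Otherwise, before pre-implementation enrolment starts:

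- **Add, do not move.** Put child age band, caregiver age band, relation to the child, education band, procedure and phase on the preoperative APAIS form, identically in both phases and after the APAIS questions. Use no name, email or code.
- **Keep every Section 3.3 item in the post-discharge survey**, so that the primary outcome can still be adjusted among responders. Leave income and usual work hours there only.
- **Name the analysis in Section 4.** Compare APAIS between phases with adjustment for the added items.
- **Report non-response.** For each phase, give links sent, surveys returned, and the distribution of the repeated items in responders against all enrolled caregivers. Because responders are a subset of those enrolled, subtracting counts in each band describes the non-responders as a group without any link.

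The cost is a minute or so of extra questions before surgery and an ethics amendment. Bands must be coarse enough that the repeated items cannot be used to match the two forms, which also limits how finely the adjustment can work. If the change comes after pre-implementation enrolment has begun, families already enrolled will lack the items and the phases will not be comparable on them.
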